## 7.2 Rationale for this Study

Pegloticase (KRYSTEXXA, a recombinant modified mammalian urate oxidase [uricase]), is approved by the United States FDA and the European Commission for use in patients with gout, at a dose of 8mg IV every two weeks. Pegloticase is efficacious in reducing sUA levels and improving clinical signs and symptoms of gout. Pegloticase provides medical benefits by lowering sUA and eliminating tophi in patients who currently have no therapeutic options. The pooled response rate for pegloticase 8 mg at 6 months is 42%, based on at least 80% of the sUA values being less than 6 mg/dL at both the 3 month and 6 month time points, with placebo response rates of 0%, a difference that was clinically important and statically significant.

Currently, pegloticase is FDA approved for intravenous administration over no less than 120 minutes [KRYSTEXXA Full Prescribing Information]. Pegloticase needs to be re-administered every two weeks to achieve optimal therapeutic outcomes and prevent elevations in sUA levels and reduce tophus burden [Baraf 2013]. Compliance with such a regimen can be burdensome and pose a barrier to treatment for some patients who may otherwise benefit from the infusion. Therefore, there is an unmet need for patients with uncontrolled gout to have access to a therapy that is effective with limited AEs, amenable to high patient compliance over several months. Administering pegloticase over a shorter duration time may address this unmet need.

One concern, however, is that a shorter infusion duration may lead to increased AEs. Pegloticase has been associated with IRs, including anaphylaxis. In a Phase 2 study in which pegloticase was administered at 30 minutes in the majority of subjects, 44% of subjects experienced an IR (no subjects experienced anaphylaxis). It is important to note that there was no methotrexate as part of the protocol and the majority of subjects did not receive any IR prophylaxis. In Phase 3 studies (which included IR prophylaxis for all subjects), with pegloticase administered over 120 minutes, IRs occurred in 26% of subjects receiving pegloticase compared to 5% of subjects receiving placebo and anaphylaxis was reported in 5% of subjects receiving pegloticase and 0% of subjects receiving placebo (pegloticase (KRYSTEXXA) Investigator's Brochure). The nature and the severity of the IRs in the Phase 2 and Phase 3 studies were relatively similar. These AEs are thought to be related to the development of anti-drug antibodies and can be reduced by avoiding infusions in patients who initially respond and then have a rebound of their serum uric acid above 6 mg/mL. These anti-drug antibodies are also associated with loss of efficacy as reflected in this increase in sUA levels [Schellekens 2005; Sundy et al, 2011].

Reducing anti-drug antibodies via pre-treatment with and concomitant administration of an immune-modifying drug, methotrexate (MTX), has been shown to be useful in other infused products, such as infliximab, in the setting of rheumatoid arthritis treatment. Based on results from MIRROR RCT (NCT03994731), pretreatment and coadministration of pegloticase with methotrexate 15 mg orally once weekly was shown to significantly reduce failure rates and the incidence of infusion reactions in patients with chronic gout as compared to pegloticase alone [Botson et al, 2022].

To address the possibility of increased AEs with a shorter infusion duration, this study will incorporate an IR prophylaxis regimen as well as pre-treatment and concomitant use of MTX with pegloticase [Hershfield et al, 2014].

Individual subject sUA Discontinuation Criteria will also be in place to minimize the potential for AEs in subjects who are non-responders to treatment. Since the risk of anaphylaxis and IRs is higher in patients who have lost therapeutic response, this study will also discontinue treatment if sUA levels increase to above 6 mg/dL at 2 consecutive study visits to minimize the potential for such AEs.

### **7.3 Rationale for Dose Selection**

The current approved dose of pegloticase for intravenous infusions, 8 mg every 2 weeks, will be tested in this study. Refer to the current version of the FDA-approved KRYSTEXXA Full Prescribing Information.

The study will be initiated enrolling subjects assigned to 60-minute infusion durations. Based on tolerability, this infusion duration may be progressively shortened to 45-minute and 30-minute infusions. A previous trial (n=41) was conducted using 30 minute and 60 minute infusions. The adverse event profile was similar in nature and severity to that which is seen with the FDA-approved 120 minute infusions [Sundy et al, 2008]. The consistent adverse event profile supports initiating this trial with subjects receiving infusions at 60 minute durations and progressively moving to shorter durations of 45 minutes and 30 minutes.

## **8 STUDY OBJECTIVES**

The overall objective of this study is to assess the tolerability and efficacy of pegloticase administered with a shorter infusion duration in subjects with uncontrolled gout receiving methotrexate.

### Primary Objective

The primary objective is to assess the tolerability of pegloticase infusions administered with methotrexate (MTX) from Day 1 through Week 24 in the cohort chosen to be most desirable duration for infusion, as measured by the incidence of IRs (including anaphylaxis) related to pegloticase.

[figure not shown]
### Secondary Objectives

The secondary objectives will be assessed for the cohort chosen to be the most desirable duration for infusion and include:

- Estimate the response rate at Month 6 (Weeks 20, 22 and 24), as measured by the sustained normalization of sUA to <6 mg/dL for at least 80% of the time during Month 6.
- Assess the proportion of subjects receiving pegloticase with MTX who experienced any of the following events: Infusion Reaction (IR) leading to discontinuation of treatment, anaphylaxis, or meeting Individual Subject sUA Discontinuation Criteria.

- Assess the time to any of the following events: IR leading to discontinuation of treatment, anaphylaxis, or meeting Individual Subject sUA Discontinuation Criteria (two consecutive pre-infusion SUAs >6 mg/dL).

#### Exploratory Objectives

- Assess the pharmacokinetics of pegloticase.
- Assess the profile of anti-uricase antibodies and anti-poly (ethylene glycol) antibodies.

#### Safety Objectives

- Assess the incidence of adverse events of special interest (AESI), including IRs, anaphylaxis, gout flares, cardiovascular events and the AE/SAE profile overall.
- Assess the proportion of subjects who experienced IR leading to slowing down of the infusion rate or discontinuation of treatment.
- Assess the time to first IR leading to slowing down of the infusion rate or discontinuation of treatment.
- Assess the time to first IR.
- Assess the proportion of subjects who were able to complete all infusions over the assigned treatment duration length or a lesser time, without clinically requiring an increased infusion time.
- Assess the proportion of infusions completed over the assigned duration length or a lesser time, without clinically requiring an increased infusion time.
- Laboratory tests and 12-lead electrocardiogram (ECG).
- Vital signs and physical examinations.

## **9 INVESTIGATIONAL PLAN**

### **9.1 Overall Study Design and Plan**

This study is a Phase 4, multicenter, open-label, infusion duration, study of pegloticase administered over < 120 minutes in combination with MTX to evaluate the safety, tolerability and efficacy in treating adult subjects with uncontrolled gout.

Approximately 10 subjects in each cohort are planned to be enrolled initially. If deemed safe, an additional 100 subjects to be enrolled in the selected cohort in order to have approximately 110 subjects exposed. Treatment duration with pegloticase will be approximately 24 weeks.

The study design will include: 1) a Screening Period, lasting up to 35 days; 2) a 4-week MTX Run-in Period; 3) a 24-week Pegloticase + MTX Period which includes an End-of study Week 24/Early Termination Visit; 4) a safety Follow-up Phone/Email 30 days after the last pegloticase infusion and 5); a 3-month Post-Treatment Follow-up.

### **Guidance on Blood Glucose Monitoring:**

HbA1c testing must be performed at Screening for all subjects (locally or centrally): If HbA1c >6.5% and/or if subject has known diagnosis of diabetes mellitus, additional measures are recommended:

- Investigator asked to closely monitor glucose levels and adjust any diabetic medications as necessary
- Subject should consult their primary care physician and/or Endocrinologist managing their diabetes

The pre-infusion IV steroid dose may be reduced (e.g., methylprednisolone 75 mg IV) after consulting with the Horizon Medical Monitor.

All subjects who meet eligibility criteria at Screening will begin oral MTX at a dose of 15 mg weekly for 4 weeks prior to the first dose of pegloticase.

Subjects will also take folic acid 1 mg orally every day beginning at Week -4 (the start of MTX) continuing until prior to the End of Pegloticase Infusion Visit (if applicable) or the Week 24/End of Study/Early Termination Visit. Subjects must be able to tolerate MTX at a dose of 15 mg during the 4-week MTX Run-in Period (prior to Day 1) to be eligible to participate in the Pegloticase + MTX Period. Subjects who are unable to tolerate MTX at a dose of 15 mg during the MTX Run-in Period will be considered screen failures and not proceed to pegloticase dosing.

Female subjects who take at least one dose of MTX and who are of childbearing potential, will receive a safety Follow-up phone call/e-mail approximately 30 days after the last dose of MTX to verify at least one ovulatory cycle has occurred after the last dose of MTX. If the subject has not ovulated, a urine pregnancy test will be performed. For male subjects who take at least one dose of MTX and who are non-vasectomized an inquiry will be conducted at the Post-Treatment 3-month Follow-up visit (or 3 months after the subject's last dose of MTX) after MTX discontinuation regarding partner pregnancy.

All subjects who complete the Run-In Period and meet the inclusion/exclusion criteria will receive the first pegloticase infusion on Day 1. All subsequent doses and study visits will be scheduled based on the Day 1 visit date.

It is required that before a subject begins the Pegloticase + MTX Period, he or she has been taking at least one protocol standard gout flare prophylaxis regimen (i.e. colchicine and/or

NSAIDs and/or low-dose prednisone  $\leq 10$  mg/day) for  $\geq 1$  week before the first dose of pegloticase and continuing flare prophylaxis per American College of Rheumatology guidelines [Khanna D et al. 2012].

For IR prophylaxis, fexofenadine (180 mg orally) will be taken the day before each infusion; fexofenadine (180 mg orally) and acetaminophen (1000 mg orally) will be taken the morning of each infusion; and methylprednisolone (125 mg IV) given over an infusion duration between 10 - 30 minutes, immediately prior to each infusion.

During the Pegloticase + MTX Period, all subjects will receive pegloticase 8 mg every 2 weeks administered IV for a total of 12 infusions from Day 1 through Week 22, inclusive for a total of 12 infusions; pegloticase will be administered after all pre-dose study visit assessments have been completed at each visit. The date and start and stop time of infusion will be recorded. sUA Discontinuation Criteria will be applied: subjects with sUA level  $> 6$  mg/dL at 2 consecutive study visits beginning with the Week 2 Visit will discontinue treatment but continue on study as described in Section 9.4.3.

Up to three pegloticase infusion durations may be assessed for the Pegloticase + MTX Period:

- 60-minute infusion
- 45-minute infusion
- 30-minute infusion

Initially, cohorts of approximately 10 subjects will be enrolled sequentially at progressively shorter infusion durations initially, beginning with the 60-minute infusion duration, progressing down to the 45-minute infusion duration and then to the 30-minute infusion duration. If deemed safe, enrollment will continue in the chosen infusion duration cohort until approximately 110 subjects are enrolled (e.g. targeted 110 subjects in the 30-minute infusion cohort, unless 30-minute infusion is not tolerated, then approximately 110 subjects may be enrolled in the 45-minute or 60-minute infusion cohort). The most desirable infusion duration is the shortest duration which is shown to be safe and well tolerated.

After the first 3 subjects at each infusion duration complete at least 4 weeks of Pegloticase + MTX period (3 infusion visits), a holistic safety assessment will be performed by the internal Safety Review Committee on available subjects' data. Study enrollment will not be paused. If a subject discontinues treatment or study prior to the third infusion visit, their available data is still included in the safety assessment. If the safety assessment indicates that the infusion duration is well tolerated (based on pre-determined criteria, see Section 9.2), then additional safety assessments will continue to be performed based on available subjects' data after 6 subjects and 10 subjects complete at least 4 weeks of the Pegloticase + MTX period (3 infusion visits).

If the Safety Review Committee confirms that the percentage of subjects meeting infusion speed-limiting criteria is less than the threshold specified in Section 9.2, then enrollment of subjects at the next progressively shorter infusion duration cohort (15 minutes shorter duration) will begin. Further, if the Safety Review Committee confirms that the percentage of subjects meeting infusion speed-limiting criteria are less than the thresholds specified in Section 9.2, then

additional subjects will be enrolled (for a total of approximately 110 subjects in the given cohort).

If any of the safety assessments indicate that a specific infusion duration is not tolerated based on pre-determined criteria, then the study may enroll additional subjects at any infusion durations. In the event that the initial 60-minute infusion duration is not tolerated based on pre-determined criteria, then the study may be revised or terminated (after internal review and assessment).

If >10 subjects are enrolled at any infusion duration, additional safety assessments will be performed when 15 subjects and 20 subjects complete at least 4 weeks of the Pegloticase + MTX period (3 infusion visits).

Once all subjects have at least 4 weeks of Pegloticase + MTX period (3 infusion visits), additional safety assessments will be done as needed (refer to the Safety Review Committee charter). If a subject discontinues treatment or study prior to either of these time-points, their available data is still included in the safety assessment.

The Safety Review Committee can modify the number of subjects at the chosen infusion duration, if they determine that more safety data is needed.

Investigators will be permitted to adjust the duration of the infusion at a particular infusion visit regardless of initial treatment duration assignment, if needed. The decision to modify the infusion duration at a visit, will be allowed based on the investigator's discretion, after a discussion with the Medical Monitor.

Subjects may return to the original infusion duration for subsequent infusions at investigator's discretion.

Pegloticase will be administered after all pre-dose study visit assessments have been completed at each visit. The date and time of infusion start and stop will be recorded.

During the Pegloticase + MTX Period, subjects will be instructed to take MTX weekly on the same day each week, within 1 to 3 days prior to each pegloticase infusion and one additional weekly dose after the last infusion for subjects who have not stopped pegloticase due to sUA Discontinuation Criteria; however, if a subject does not do so, MTX must be taken  $\geq 60$  minutes prior to each pegloticase infusion.

After Day 1, if a subject becomes unable to tolerate 15 mg of MTX, the MTX dose may be reduced and/or discontinued and the subject may remain in the study (see [Section 9.5.7.3.2.2](#)).

Samples for measurement of sUA levels, PK analysis of pegloticase, pegloticase immunogenicity and MTX Polyglutamate analysis will be collected at visits indicated in the Schedule of Assessments ([Section 2.1](#)).

Safety assessments, including monitoring and recording of all AEs, whether or not drug-related, measurement of vital signs, physical examinations and monitoring of hematology and blood chemistry, will be performed.

[figure not shown]
The total blood volume to be collected from each subject during this study is approximately 450 mL.

An External Adjudication Committee will be established for this study to adjudicate the AESIs. The External Adjudication Committee will be comprised of external experts with experience in immunology, allergic reactions, rheumatology and/or cardiovascular diseases. Details outlining the responsibilities of the Adjudication Committee will be included in the Adjudication Committee charter. AESIs defined in the protocol (See Section 9.6.1.2.1.5) include IRs, anaphylaxis and cardiovascular events. The AESI of gout flare will not be adjudicated.

Aggregate safety data will be reviewed by the internal Safety Review Team (SRT) and Safety Review Committee (SRC). Subject safety and tolerability of the pegloticase regimen will be discussed to establish a recommendation as whether to continue the current treatment regimen or to modify the assigned treatment regimen.

The SRC will be comprised of members of the Horizon Clinical Development and Patient Safety and Pharmacovigilance Teams. Meetings will occur at pre-determined timepoints or ad-hoc dependent on any potential safety signals reported (e.g. anaphylaxis or any SAE related to pegloticase infusion). If any anaphylaxis event or SAE related to pegloticase infusion occurs with any subject, real-time with expedited review of patient profiles and/or relevant data available in the electronic data capture will occur. Changes may include, but are not limited to, increasing the pegloticase infusion duration or modifying the methotrexate dosage. An overview of the study design is presented in the schematic below and details of study activities are provided in Section 9.1.

**Figure 9.1 Schematic of Study Design**

IV = intravenous; MTX = methotrexate; PO = oral; Q2W = every 2 weeks; W = week

Note: Study visits must be completed within  $\pm 3$  days of the target visit date.

1. Prior to the Treatment Period, subjects will begin taking at least one of the per protocol standard gout flare prophylaxis regimen (colchicine 0.6 mg/day and/or NSAID and/or low dose prednisone <10 mg/day) for  $\geq 1$  week before the first dose of pegloticase and continuing flare prophylaxis throughout the pegloticase treatment period per American College of Rheumatology guidelines. For IR prophylaxis, fexofenadine (180 mg orally) will be taken the day before each infusion; fexofenadine (180 mg orally) and acetaminophen (1000 mg orally) will be taken the morning of each infusion; and methylprednisolone (125 mg IV) over an infusion duration between 10 and 30 minutes, will be administered immediately prior to each infusion.
2. Stopping rules will be implemented: Subjects with 2 sUA levels  $> 6$  mg/dL at 2 consecutive study visits beginning with the Week 2 Visit will discontinue from pegloticase therapy and complete the End of Pegloticase Infusions Visit and remain on study.
3. The determination on whether to enroll the next cohort of subjects to a different infusion duration level will be based on whether the previous cohort meets the Infusion Speed-Limiting Criteria as well as the Safety Review Committee decision.
4. All subjects will receive a safety follow-up phone call/e-mail approximately 30 days after the last dose of pegloticase to assess if any SAEs have occurred. If the subject discontinues treatment but continues in the study, then this follow-up visit may be replaced by a scheduled study visit.

## 9.2 Infusion Speed-Limiting Criteria

Infusion speed-limiting criteria will be met if a subject experiences any severe (Grade  $\geq 3$ ) IRs or any other severe AEs within 24 hours of receiving pegloticase infusion and attributed to the infusion and not any other underlying disease process. The signs and symptoms of the severe IRs are usually prolonged (e.g., not rapidly responsive to symptomatic medication and/or brief

interruption of infusion) or recurrent following initial improvement. Possible associated signs and symptoms of IRs may include but not limited to:

- Respiratory: difficulty breathing with wheezing or stridor; upper airway swelling (lip, tongue, throat, uvula, or larynx); respiratory distress manifested as at least 2 or more of the following: tachypnoea, increased use of accessory respiratory muscles, cyanosis, recession, grunting
- Cardiovascular: hypertension, tachycardia, measured hypotension, a decreased level of consciousness, loss of consciousness
- Dermatological or mucosal: generalized urticaria (hives) or generalized erythema, angioedema, generalized pruritus with skin rash

If  $\leq$  one-eighth of subjects meet infusion speed-limiting criteria at the same infusion duration after 3 subjects and after 6 subjects, then enrollment may continue at the same infusion duration. If  $\leq$  one-third of subjects meet infusion speed-limiting criteria at the same infusion duration after 10 subjects, then enrollment may continue at the next progressively shorter infusion duration.

If  $>$  one-eighth of subjects meet infusion speed-limiting criteria, then enrollment at that infusion duration may be suspended.

Safety Review Committee must confirm that infusion speed-limiting criteria were met, prior to additional patients being enrolled at the previous infusion duration. In the event that  $>$  one-eighth of subjects meet infusion-speed limiting criteria at the initial 60-minute infusion duration, then the study may be revised or terminated (after internal review and assessment).

If an anaphylaxis event occurs in any subject, further dosing with pegloticase for that subject will be terminated.

If any anaphylaxis event or SAE related to pegloticase infusion occurs with any subject, all pertinent data will be provided for expedited review to the Adjudication Committee (for the purpose of adjudicating AESIs) and the SRT/SRC.

If any anaphylaxis event or SAE related to pegloticase infusion occurs with any subject, real-time with expedited review of patient profiles and/or relevant data available in the electronic data capture will occur.

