Up to three pegloticase infusion durations will be assessed in the Pegloticase + MTX Period: 60-minute infusion, 45-minute infusion and 30-minute infusion. Initially, cohorts of approximately 10 subjects will be enrolled sequentially at progressively shorter infusion durations, beginning with the 60-minute infusion duration, progressing down to the 45-minute infusion duration and then to the 30-minute infusion duration. If deemed safe, enrollment will continue in the chosen infusion duration cohort until approximately 110 subjects are enrolled (e.g. targeted 110 subjects in the 30-minute infusion cohort, unless 30-minute infusion is not tolerated, then approximately 110 subjects may be enrolled in the 45-minute or 60-minute infusion cohort). The most desirable infusion duration is the shortest duration, which is shown to be safe and well tolerated.

After the first 3 subjects at each infusion duration complete at least 4 weeks of the Pegloticase + MTX period (3 infusion visits), a holistic safety assessment will be performed by the internal Safety Review Committee on available subjects' data. Study enrollment will not be paused. If a subject discontinues treatment or study prior to the third infusion visit, their available data is still included in the safety assessment. If the safety assessment

indicates that the infusion duration is well tolerated (based on pre-determined infusion speed-limiting criteria as described in Section 9.2), then additional safety assessments will continue to be performed based on available subjects' data after 6 subjects and 10 subjects complete at least 4 weeks of the Pegloticase + MTX period (3 infusion visits).

If the Safety Review Committee confirms that the percentage of subjects meeting infusion speed-limiting criteria are less than the thresholds specified in Section 9.2, then enrollment of subjects at the next progressively shorter infusion duration cohort (15 minutes shorter duration) will begin. Further, if the Safety Review Committee confirms that the percentage of subjects meeting infusion speed-limiting criteria are less than the thresholds specified in Section 9.2 then additional subjects will be enrolled (for a total of approximately 110 subjects in the given cohort).

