### **Infusion Speed-Limiting Criteria:**

Infusion speed-limiting criteria will be met if a subject experiences any severe (Grade  $\geq 3$ ) IRs or any other severe AEs within 24 hours of receiving pegloticase infusion and attributed to the infusion and not any other underlying disease process. The signs and symptoms of the severe IRs are usually prolonged (e.g., not rapidly responsive to symptomatic medication and/or brief interruption of infusion) or recurrent following initial improvement. Possible associated signs and symptoms of IRs may include but not limited to:

- Respiratory: difficulty breathing with wheezing or stridor; upper airway swelling (lip, tongue, throat, uvula, or larynx); respiratory distress manifested as at least 2 or more of the following: tachypnoea, increased use of accessory respiratory muscles, cyanosis, recession, grunting
- Cardiovascular: hypertension, tachycardia, measured hypotension, a decreased level of consciousness, loss of consciousness
- Dermatological or mucosal: generalized urticaria (hives) or generalized erythema, angioedema, generalized pruritus with skin rash

If  $\leq$  one-eighth of subjects meet infusion speed-limiting criteria at the same infusion duration after 3 subjects and after 6 subjects, then enrollment may continue at the same infusion

duration. If  $\leq$  one-eighth of subjects meet infusion speed-limiting criteria at the same infusion duration after 10 subjects, then enrollment may continue at the next progressively shorter infusion duration.

If  $>$  one-eighth of subjects meet infusion speed-limiting criteria, then enrollment at that infusion duration may be suspended. The Safety Review Committee must confirm that infusion speed-limiting criteria were met, prior to additional patients being enrolled.. In the event that  $>$  one-eighth of subjects meet infusion-speed limiting criteria at the initial 60-minute infusion duration, then the study may be revised or terminated (after internal review and assessment).

If an anaphylaxis event occurs in any subject, further dosing with pegloticase for that subject will be terminated.

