### **9.7.9 Sample Size and Power Considerations**

Initially, cohorts of approximately 10 subjects are planned to be enrolled sequentially at progressively shorter infusion durations beginning with 60-minute infusion duration, progressing down to the 45-minute duration and then to the 30-minute infusion duration. Approximately 110 subjects are planned to be enrolled into the selected infusion cohort. Therefore, the minimum number of subjects enrolling across the 3 different cohorts in the study is approximately 130.

Based on the MIRROR-RCT study, we expect approximately 5.0% of subjects to have an IR (including events of anaphylaxis) when taking pegloticase concurrently with MTX. The sample size of 110 for the selected cohort is chosen to ensure a high probability of ruling out an unacceptably high IR rate. If the observed IR rate is 5%, there is a greater than 80% probability that the upper bound of the two-sided 95% exact confidence interval for the IR rate is less than 13%.

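### Section 9.2 sets the 10-subject step-down limit at one-third where the synopsis and the rest of Section 9.2 use one-eighth, so 2 or 3 of 10 meets both the go and the stop condition

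*Protocol*

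**What the plan says.** The speed-limiting criteria count subjects with a Grade 3 or higher infusion reaction, or another severe adverse event, within 24 hours of an infusion and attributed to it. The protocol states the limit for the 10-subject decision in two places.

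- Section 9.2: the study may shorten the infusion if no more than "one-third of subjects meet infusion speed-limiting criteria at the same infusion duration after 10 subjects, then enrollment may continue at the next progressively shorter" duration.
- Synopsis, Infusion Speed-Limiting Criteria: the same step is allowed if no more than "one-eighth of subjects meet infusion speed-limiting criteria at the same infusion duration after 10 subjects, then enrollment may continue at the next progressively shorter" duration.

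The other limits in Section 9.2 are all one-eighth. That is the limit at the 3- and 6-subject looks. If more than "one-eighth of subjects meet infusion speed-limiting criteria, then enrollment at that infusion duration may be suspended". If more than "one-eighth of subjects meet infusion-speed limiting criteria at the initial 60-minute infusion duration, then the study may be revised or terminated", after internal review.

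The design text gives no number of its own and points to Section 9.2. In Section 9.1 the next cohort opens once the Safety Review Committee confirms that the percentage "is less than the threshold specified in Section 9.2, then enrollment of subjects at the next progressively shorter infusion duration cohort". The synopsis study design says the same of percentages that "are less than the thresholds specified in Section 9.2, then enrollment of subjects at the next progressively shorter infusion duration cohort". SAP Section 1.1.2 also refers to protocol Section 9.2 for the tolerability criteria and states no threshold. Note 3 to Figure 9.1 makes the move "based on whether the previous cohort meets the Infusion Speed-Limiting Criteria as well as the Safety Review Committee decision".

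**The concern.** One decision has two limits, and the looser one is in the section that the rest of the plan cites for the number. The decision matters because each step down, from 60 to 45 minutes and from 45 to 30, exposes new subjects to a faster infusion of a drug whose main known risks include infusion reactions and anaphylaxis.

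As written, a 60-minute cohort with 2 or 3 of 10 subjects meeting the criteria qualifies for shortening to 45 minutes and also for revising or terminating the study. At 45 minutes the same result qualifies for the move to 30 minutes and for suspending enrollment at 45. No reason is given for a limit at the step-down that is looser than at the two earlier looks. A site, an IRB or an inspector could not say from the text whether a step-down at 2/10 or 3/10 followed the protocol.

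The sentence does not govern expansion of the 30-minute cohort to about 110 subjects.

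**Working it through.** **Inputs.** The decision is taken on 10 subjects with at least 3 infusions each (Section 9.7.8). The go limit is one-third (Section 9.2) or one-eighth (synopsis). The stop limit is above one-eighth (Section 9.2). The limit at 3 and 6 subjects is one-eighth (Section 9.2). The plan gives no operating characteristics for this rule, so there is no stated figure to reproduce.

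**Step 1: turn the fractions into counts.**

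| Subjects | One-eighth | Most allowed | One-third | Most allowed |
|---|---|---|---|---|
| 3 | 0.375 | 0 | 1 | 1 |
| 6 | 0.75 | 0 | 2 | 2 |
| 10 | 1.25 | 1 | 3.33 | 3 |

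At 10 subjects neither limit is a whole number, so reading it as at most (Section 9.2) or as less than (Section 9.1) gives the same counts.

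**Step 2: find the overlap.** 2/10 = 20% and 3/10 = 30%. Both are below 33.3% (go) and above 12.5% (stop). With one-eighth in both places, 0 or 1 of 10 is go, 2 or more is stop, and nothing overlaps.

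**Step 3: choose true rates.** The documents give no rate for subjects meeting the criteria. The nearest figure is in Section 9.7.9: "we expect approximately 5.0% of subjects to have an IR (including events of anaphylaxis) when taking pegloticase concurrently with MTX". That covers reactions of any grade, so 5% is used here only as an illustration. The other two assumed rates are 12.5% (the threshold) and 20%.

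**Step 4: the 10-subject look alone.** Let X be binomial with n = 10 and rate p. At p = 0.05:

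- P(X ≤ 1) = 0.95^10 + 10 × 0.05 × 0.95^9 = 0.5987 + 0.3151 = 0.914
- P(X = 2 or 3) = 45 × 0.05² × 0.95^8 + 120 × 0.05³ × 0.95^7 = 0.0746 + 0.0105 = 0.085

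| Assumed true rate | Go under one-eighth, P(X ≤ 1) | Go under one-third, P(X ≤ 3) | Overlap, P(X = 2 or 3) |
|---|---|---|---|
| 5% | 0.9139 | 0.9990 | 0.0851 |
| 12.5% | 0.6389 | 0.9725 | 0.3336 |
| 20% | 0.3758 | 0.8791 | 0.5033 |

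**Step 5: earlier looks applied strictly.** One event among 3 or among 6 already exceeds one-eighth (33% and 17%), so the first 6 subjects must have no events, with probability (1 − p)^6. Let Y be binomial with n = 4 for subjects 7 to 10. The chance of step-down is (1 − p)^6 × P(Y ≤ 1) under one-eighth and (1 − p)^6 × P(Y ≤ 3) under one-third. At p = 0.05, 0.95^6 = 0.7351 and P(Y ≤ 1) = 0.9860, giving 0.7248. P(Y ≤ 3) is almost 1, giving 0.7351.

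| Assumed true rate | Step-down under one-eighth | Step-down under one-third | Added by one-third |
|---|---|---|---|
| 5% | 0.7248 | 0.7351 | 0.010 |
| 12.5% | 0.4134 | 0.4487 | 0.035 |
| 20% | 0.2147 | 0.2617 | 0.047 |

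Step 5 treats the first 6 subjects as event-free once they pass their look. They are assessed after 3 of 12 infusions and can have events later, so these figures are not a firm lower limit.

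**The case against.** The strongest reply is that the intended limit is not in doubt. The Summary Table of Changes records a move to one-eighth throughout the protocol after FDA feedback, and every other limit in Section 9.2 and in the synopsis criteria is one-eighth. One-third looks like leftover text. That is probably right, and it settles which way to correct the sentence. It does not make the current Section 9.2 correct: a committee that follows the cross-reference still reads one-third.

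Second, every limb in Section 9.2 says *may*, and step-down needs a committee decision, so nothing compels the study to proceed at 2/10 or 3/10. This stands, and it limits the consequence. However, Section 9.1 and the synopsis say enrollment at the shorter duration will begin once the committee confirms the result is below the Section 9.2 threshold, so the number it confirms against matters.

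Third, the two limbs concern different actions: shortening for new subjects, and suspending at the current duration. The clash is indeed most direct at 60 minutes. At 45 minutes, though, going faster while suspending the slower infusion on the same safety result is no more coherent.

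Fourth, the strict-look figures are small. This is fair; the size depends mainly on how strictly the 3- and 6-subject looks are applied.

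Finally, the protocol version in hand is dated November 2022 and the first is dated April 2020, so both step-downs may already have been decided. The documents do not say. The threshold also plays no part in the primary analysis or in the choice of 110 subjects.

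**Conclusion.** The concern holds. Section 9.2 contradicts the synopsis and its own stop clauses on a subject-safety threshold, and 2 or 3 of 10 meets both the go and the stop condition. The contradiction follows from the text and needs no assumption.

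Its practical size does depend on assumed true rates of 5% to 20%. The overlap has a chance of 8.5% to 50% on the 10-subject look alone. If the earlier looks are strictly enforced, the looser limit adds 1.0 to 4.7 percentage points to the chance of step-down. Committee discretion lowers the risk that a step-down would actually follow, but does not resolve which limit applies. Because the error sits in the controlling section of a safety rule and can be removed with one phrase, it must be fixed.

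**What to change.** In the 10-subject sentence of Section 9.2, replace one-third with one-eighth and state the count. Suggested text: *If ≤ one-eighth of subjects (at most 1 of 10) meet infusion speed-limiting criteria at the same infusion duration after 10 subjects, then enrollment may continue at the next progressively shorter infusion duration.*

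An amendment or clarification letter is enough. Sample size, procedures and analyses are unchanged. The cost is a lower chance of step-down when the infusion is in fact well tolerated: at an assumed true rate of 5% it falls from 99.9% to 91.4% on the 10-subject look alone, or from 73.5% to 72.5% with the earlier looks applied strictly.
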